6.3.7. Immune Response to Dystrophin/Mini-dystrophin and to AAV9

Endpoints:

- Immune response: ADA and T cell response to mini-dystrophin transgene protein
- Immune response: ADA, NAb and T cell response to AAV9 capsid

Analysis:

- Analysis set: Safety Analysis Set (through Week 52) ([Section 4](#)).
- Analysis methodology: Not applicable.
- Missing data: All available data in the reporting period will be included. Missing data will not be imputed.
- The number and percent of participants who are (1) ADA-positive to mini-dystrophin transgene protein, (2) T cell response-positive to mini-dystrophin transgene protein by peptide pool (3) ADA-positive to AAV9, (4) NAb-positive to AAV9, and (5) T cell response-positive to AAV9 by peptide pool will be provided by visit, and an overall number and percent of participants who are positive at any post-screening visit for fordadistrogene movaparvovec and placebo.
- The observed titers for ADA-positive to mini-dystrophin participants, ADA-positive to AAV9 participants and NAb-positive to AAV9 participants will be summarized (N, mean, SD, median, Q1, Q3, minimum, and maximum) by visit for fordadistrogene movaparvovec and placebo.
- The observed levels for participants who have positive T cell response to mini-dystrophin transgene protein and T cell response to AAV9 will be summarized (N, mean, SD, median, Q1, Q3, minimum, and maximum) by peptide pool and visit for fordadistrogene movaparvovec and placebo.
- Analysis windows for these summaries are provided in [Appendix 2.1](#), Note that unplanned visits will be included in the overall summaries only.
- Listings of the positive/negative status and associated observed titers/observed levels for the immunogenicity endpoints listed above by visit for fordadistrogene movaparvovec and placebo.

Graphical display:

- Box-plots for observed titers for ADA-positive and NAb-positive participants will be presented by visit for fordadistrogene movaparvovec and placebo.
- Box-plots for observed levels for participants with positive T cell response to mini-dystrophin transgene protein and positive T cell response to AAV9 capsid will be presented by peptide pool and visit for fordadistrogene movaparvovec and placebo.

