	Change from Baseline at Week 52 in the Modified PODCI: Sports and Physical Functioning Core Scale (Pediatric Parent).	Population-level summary: difference in means between fordadistrogene movaparovec and placebo for each secondary endpoint.

Objectives	Endpoints	Estimands
Tertiary/Exploratory:	Tertiary/Exploratory:	
To assess the systemic immune response (humoral and cellular) to dystrophin in participants treated with fordadistrogene movaparvovec	Immune response (anti-drug antibodies (ADA) to mini-dystrophin and enzyme-linked immune absorbent spot (ELISpot)) to mini-dystrophin through Year 1 Week 52.	N/A
To assess the systemic immune response (humoral and cellular) to the AAV9 capsid in participants treated with fordadistrogene movaparvovec	Immune response (ADA, ELISpot, and NAb) to AAV9 through Year 1 Week 52.	N/A
To characterize the change in ankle range of motion in participants treated with fordadistrogene movaparvovec as compared to placebo.	Change from Baseline at Week 52 in passive ankle range of motion (dorsiflexion).	N/A
To characterize real-life function in participants treated with fordadistrogene movaparvovec as compared to placebo.	Change from Baseline at Week 52 in real-life function parameters as assessed by actigraphy.	N/A
To tabulate loss of ambulation in participants treated with fordadistrogene movaparvovec compared to placebo.	Loss of ambulation through Week 52.	N/A
To characterize pulmonary function in participants treated with fordadistrogene movaparvovec as compared to placebo.	Change from Baseline at Week 52 in %pFVC.	N/A
To characterize health-related quality of life in participants treated with fordadistrogene movaparvovec as compared to placebo	Response to each of the 5 dimensions of the EQ-5D-Y proxy assessment at Week 52	N/A
	Change from Baseline at Week 52 on the EQ visual analog scale (VAS) proxy assessment.	N/A
To characterize caregiver health-related QoL in caregivers of participants treated with fordadistrogene movaparvovec as compared to placebo.	Response to each of the 5 dimensions of the EQ-5D-5L assessment at Week 52.	N/A
	Change from baseline at Week 52 in the EQ-5D-5L VAS assessment.	N/A
	Change from baseline at Week 52 in the EQ-5D-5L index score.	N/A
To evaluate viral vector shedding following a single administration of fordadistrogene movaparvovec.	Quantification of viral vector shedding kinetics of fordadistrogene movaparvovec in whole blood, saliva and urine.	N/A

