2.3.2. Treatment Groups and Reporting Periods for Analysis

In the study schematic in Figure 1, the study period and treatment groups to be included in the primary analysis are encircled in red.

- Treatment groups:
 1. fordadistrogene movaparvovec – participants randomized to Cohort 1 to receive a single dose of fordadistrogene movaparvovec on Day 1 (Year 1 Day 1).
 2. Placebo – participants randomized to Cohort 2 to receive a single dose of placebo on Day 1 (Year 1 Day 1).

- Reporting Period:

All analyses will be relative to Day 1 (Year 1 Day 1) investigational product (IP) administration.

The reporting period will include all data from the day of the Year 1 Day 1 IP administration through Week 52. Specifically, all participant data from Day 1 to the earliest of (1) Day 390 (the upper limit of the Week 52 analysis visit window or (2) one day before the Year 2 Day 1 IP administration.

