3.3.3. Immune Response Endpoints

1. Immune response (anti-drug antibodies [ADA] and T cell response) to mini-dystrophin transgene protein through Year 1 Week 52.
2. Immune response (ADA, T cell response and neutralizing antibodies [NAb]) to AAV9 through Year 1 Week 52.

ADA and NAb immune responses are provided as Positive or Negative with associated titers. ELISpot immune responses are provided for each of 3 peptide pools as Positive or Negative with associated response levels.

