3.4. Baseline Variables

3.4.1. Covariates and Stratification Variables

- Baseline for the primary endpoint: Baseline NSAA total score is defined as the last non-missing NSAA total score collected prior to Year 1 IP administration.
- Baseline for secondary and exploratory endpoints: Baseline is defined as the last non-missing assessment collected prior to Year 1 IP administration.
- Screening age (years) covariate: The screening age covariate is defined as the participant's age (as calculated based on month and year of birth) on the day of the Screening visit. Screening age will be calculated to one decimal (eg, 7 years and 4 months will be 7.3 years).
- The participant's Screening age rather than Screening age stratum will be used in all efficacy analyses, unless specified otherwise.

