6.1.1.5. Sensitivity Analysis #4

The difference between screening age and age at dosing due to pause(s) in dosing during the conduct of the study could impact the evaluation of age effect in the model. To assess this impact, a sensitivity analysis of the primary analysis would be conducted by replacing age at screening with age at dosing as the age-based covariate.

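### The overall immune-positivity count in SAP 6.3.7 does not separate boys already positive before dosing from boys who become positive after it

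*SAP*

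**What the plan says.** The objective in SAP 2.1.1 reads "To assess the systemic immune response (humoral and cellular) to the AAV9 capsid in participants treated with fordadistrogene movaparvovec", with a parallel objective for dystrophin. SAP 3.3.3 defines the endpoint by assay result alone: "ADA and NAb immune responses are provided as Positive or Negative with associated titers". T cell results are likewise positive or negative, with a level, for each peptide pool.

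SAP 6.3.7 uses the Safety Analysis Set. For each assay it gives the number and percent positive by visit and then "an overall number and percent of participants who are positive at any post-screening visit for fordadistrogene movaparvovec and placebo". On which visits feed that count it adds: "Note that unplanned visits will be included in the overall summaries only". Titers and T cell levels are summarised as observed values in positive participants. The section also provides "Listings of the positive/negative status and associated observed titers/observed levels for the immunogenicity endpoints listed above by visit".

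Two other sections bear on this. On timing, 2.3.2 states: "The reporting period will include all data from the day of the Year 1 Day 1 IP administration through Week 52". On baseline, 3.4.1 states for secondary and exploratory endpoints: "Baseline is defined as the last non-missing assessment collected prior to Year 1 IP administration". Section 6.3.7 limits its data to the reporting period but does not use the baseline definition.

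**The concern.** A boy who is positive before the infusion and stays positive adds one to the overall count, exactly as does a boy who was negative and converts. Nothing in 3.3.3 or 6.3.7 separates newly positive, boosted and unchanged results. The titer and level summaries have the same feature: a pre-existing titer enters beside newly formed ones, and no change from baseline is shown.

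At stake is how the treated-arm percentage is read. It serves an objective about response in treated boys, and a reader will naturally take it as the frequency of response after the product. To the extent that some boys were positive beforehand, it answers a different question.

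The anchor is a smaller matter. Screening precedes dosing, so post-screening and the reporting period do not describe the same span of time.

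**Working it through.** The SAP states no figure that could be reproduced here. The check is a comparison of text, followed by an illustration with assumed inputs.

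**Text**

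1. Condition on pre-dose status: none in 3.3.3 or 6.3.7.
2. Baseline row: every immunogenicity window in Appendix 2.1 is post-dose. The earliest lower limit is Day 2 (ADA to mini-dystrophin), and T cell response has only Week 9, Days 50 to 70. The by-visit tables are therefore not set up to show pre-dose status.
3. Practice elsewhere in the SAP: 6.7.2 gives laboratory abnormalities for all participants and separately by normal and abnormal baseline; 6.3.5 and 6.3.6 use baseline-to-Week-52 shift tables. Immunogenicity has no counterpart.
4. Anchor: the count says post-screening, while the data rule in 6.3.7, with 2.3.2, begins on the day of dosing. The data rule removes samples taken before Day 1. It does not settle a sample drawn on Day 1 before the infusion, if there is one, because the period starts on the day and not at the infusion.

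**Illustration**

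Inputs, both assumed because the SAP gives neither:

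- q: share of boys positive before dosing who stay positive, with all other boys taken as pre-dose negative;
- p: share of pre-dose negatives who become positive after dosing.

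Overall percent positive = q + (1 - q)p. Excess over the conversion rate = q + (1 - q)p - p = q(1 - p).

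| q | p | Overall positive | Excess over p |
|---|---|---|---|
| 0% | 30% | 30% | 0 points |
| 5% | 30% | 33.5% | 3.5 points |
| 10% | 30% | 37% | 7 points |
| 20% | 30% | 0.20 + 0.80 × 0.30 = 44% | 0.20 × 0.70 = 14 points |
| 20% | 60% | 68% | 8 points |
| 20% | 90% | 0.20 + 0.80 × 0.90 = 92% | 0.20 × 0.10 = 2 points |

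For scale only, take the approximate Cohort 1 size of 66 in SAP 2.3, with q = 20% and p = 30%. The rule would count 0.44 × 66 = 29.0 boys: 0.20 × 66 = 13.2 persistent positives and 0.80 × 0.30 × 66 = 15.8 new ones. The 66 is the planned full analysis set figure; the Safety Analysis Set also takes in siblings and boys meeting exclusion criterion 15.

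With the same q and no new response, the placebo arm of about 33 would show 20%, or 6.6 boys. Treated minus placebo is then 44 - 20 = 24 points, which is (1 - q)p: new positives as a share of all boys, not the 30% conversion rate among those at risk.

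**The case against.** The strongest reply is that the SAP claims little for this count. It reports boys who are positive, in both arms and by visit, without calling them treatment-induced. A concurrent randomised placebo column shows the background, and individual results are listed. The endpoint is tertiary/exploratory, with no estimand, test or decision rule. Pre-dose positivity could be near zero, and any antibody limit at entry would be in the protocol, which is not shown. All of this stands and sets the severity. It does not answer the point itself: the placebo column and the listings let a reader see background positivity, but neither removes it from the treated-arm percentage or from the titer summaries.

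Three stronger readings are tempting, and the SAP does not support them.

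- A reader might infer that samples taken between Screening and Day 1 enter the count, so that one pre-dose T cell positive makes a responder when Week 9 is the only post-dose window. Section 6.3.7 restricts data to the reporting period, so at most a pre-infusion draw on Day 1 is unclear.
- A reader might infer from 6.1.1.5, which mentions "The difference between screening age and age at dosing due to pause(s) in dosing during the conduct of the study", that repeat pre-dose draws are likely. That section concerns the age covariate and says nothing about immunogenicity sampling.
- A reader might multiply the percentage-point excess by 66 to get a number of wrongly counted boys. The excess compares rates with different denominators (all boys, and pre-dose negatives). In the illustration the persistent positives number q × 66.

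**Conclusion.** The point holds in a limited form. As written, the overall count and the titer and level summaries do not separate persistent pre-existing positivity from immune response arising after the product, and post-screening is a loose anchor beside a reporting period that starts on the day of dosing.

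The size is unknown. It is q(1 - p), which rests on two assumed quantities: it vanishes if nobody is positive before dosing and is small if nearly everyone converts. The 14-point and 2-point figures show how the excess moves and are not estimates. The SAP does not support a statement that the reported incidence will in fact be inflated.

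Severity is minor: a cheap improvement to an exploratory, descriptive summary.

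**What to change.** In 6.3.7, replace the post-screening anchor by any visit after Year 1 Day 1 IP administration, keeping the end of the reporting period in 2.3.2. Using the 3.4.1 baseline, add one table that gives for each assay and arm (T cell response by peptide pool):

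- baseline-positive, n (%);
- newly positive after dosing, with baseline-negative participants who have a post-dose sample as denominator;
- baseline unknown, as a separate row;
- for ADA and NAb, boosted positives: baseline-positive participants whose titer rises by a stated amount. The SAP contains no basis for a particular fold-rise, so the criterion should be justified from the assay and fixed before unblinding.

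The existing overall count can stay beside these rows. The cost is a wording change, one extra exploratory table and smaller denominators. It needs no new sampling; boys without a pre-dose result go to the baseline-unknown row.

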6.3.8. Viral Vector Shedding

Samples collected for viral vector shedding are only assayed for Cohort 1 (initially fordadistrogene movaparvovec) participants.

Note that there may be participants for which sample collection may continue after 2 consecutive undetectable samples because notification to stop may be provided after the participant has had another scheduled visit where a sample was to be collected or a site may mistakenly collect a sample after receiving notification to stop sample collection.

Endpoint:

- Peak viral vector levels (vg/ml) post fordadistrogene movaparvovec administration for each of the five profiles – one without MNase treatment for whole blood, one without MNase for saliva, one with MNase for saliva, one without MNase for urine, one with MNase for urine

Analysis:

- Analysis set: Viral Vector Shedding subset of Safety Analysis Set (through Week 52) ([Section 4](#)).
- Analysis methodology: Not applicable.
- Missing data: Missing/undetectable results will not be imputed.
- N, mean, SD, median, Q1, Q3, minimum, and maximum will be provided .

Endpoint:

- Time in weeks of peak viral vector shedding post fordadistrogene movaparvovec administration for each of the five profiles – one without MNase treatment for whole blood, one without MNase for saliva, one with MNase for saliva, one without MNase for urine, one with MNase for urine

Analysis:

- Analysis set: Viral Vector Shedding subset of Safety Analysis Set (through Week 52) ([Section 4](#)).
- Analysis methodology: Not applicable.
- Missing data: Missing/undetectable results will not be imputed.
- N, mean, SD, median, Q1, Q3, minimum, and maximum will be provided.

Endpoint:

- Time in weeks to undetectable viral vector (time to clearance of viral vector) from date of fordadistrogene movaparvovec administration for each of the five profiles – one without MNase treatment for whole blood, one without MNase for saliva, one with MNase for saliva, one without MNase for urine, one with MNase for urine.
- Time in weeks to the last undetectable viral vector from date of fordadistrogene movaparvovec administration for each of the five profiles – one for whole blood, two for saliva, two for urine.

Analysis:

- Analysis set: Viral Vector Shedding subset of Safety Analysis Set (through Week 52) ([Section 4](#)).
- Analysis methodology: Time in weeks to undetectable viral vector and last undetectable viral vector will be summarized using the K-M method ([Section 5.2.2](#)). The 25th, 50th and 75th percentile of time to undetectable viral vector and last undetectable viral vector will be provided along with 95% confidence intervals based on the Breslow-Day method. The range will also be presented.
- Missing data: Missing/undetectable results will not be imputed.

Graphical displays:

- Kaplan-Meier plots of time to undetectable viral vector and time to the last undetectable viral vector for each of the five profiles – one without MNase treatment for whole blood, one without MNase for saliva, one with MNase for saliva, one without MNase for urine, one with MNase for urine

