1. VERSION HISTORY

Table 1. Summary of Changes			
Version/ Date	Associated Protocol Amendment	Rationale	Specific Changes
9 08 Apr 2024	Amendment 15 28-Dec-2023	To clarify the timing of primary analysis based on protocol	Section 5 Added text “The primary analysis will occur after at least 90 FAS participants complete Day 360 (Visit 19) or discontinued from the study prior to Week 52 if they had received Year 1 IP at least one year prior to the data cutoff.”
		Due to the transfer of the viral vector shedding assay to an internal lab during the course of the study and some differences in the results between the 2 assays, the analysis for endpoint viral vector levels are removed from the planned analysis as they may include data from both assays. switch of labs for the	Sections 6.3.8, Appendix 1 Removed analysis for viral vector levels endpoint
		To clarify the FAS definition for PCD analysis and align with protocol	Section 4 Changed the name of Full Analysis Set (FAS) to Full Analysis Set (FAS) (through Week 52) Added footnote to clarify the FAS for PCD analysis
		To evaluate the treatment effect more comprehensively using multiple endpoint	Sections 5.2.4, 6.4 Added global statistical test analysis for specified multiple functional endpoints
		To better present the analysis results	Sections 6.1.1, 6.2.2, 6.2.3, 6.2.4, 6.2.5, Appendix 1 Removed model-based summary of LS means at Week 52 for each age. Added standard error of each LS mean and estimated difference in LS mean in the summary Removed graph for Mean (SD) change from Baseline at Week 52 by age at the Screening visit.

		To update the ANCOVA analysis for biceps muscle biopsies by removing Baseline factor as the values at Baseline are expected to be around 0 and exhibit extremely low variability	Sections 6.2.1.1, 6.2.12, Appendix 1 Removed text “Baseline (continuous variable)” from the ANCOVA model
		To evaluate actigraphy endpoints based on statistical model and aid in the interpretation of the treatment effect	Section 5.4, 6.3.2, Appendix 1 Added clarification that mean will be calculated for visits with at least 4 compliant days Added MMRM analysis for all actigraphy endpoints Added 95 th percentile of cadence actigraphy endpoint for Screening age strata subgroup analysis
		To correct typographical errors in the subgroup analysis for number of skills endpoints	Section 6.4.1 Removed MMRM description for NSAA total score Added the description of Binomial with logit link function

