3.3.4. Viral Vector Shedding Endpoints

Whole blood, saliva, and urine samples for viral vector shedding kinetics will be collected in approximately the first 45 treated participants (approximately 30 treated with fordadistrogene movaparvovec and approximately 15 treated with placebo). For each randomized participant, sample collection for a particular matrix (sample type) will be stopped when at least 2 consecutive negative results are observed in that matrix.

Viral vector levels (vector genomes /ml), measuring intact and fragmented copies, will be determined in whole blood, saliva and urine using qPCR analysis. Additionally, intact viral vector levels (vector genomes/mL) in saliva and urine samples will be measured as intact copies following treatment with Micrococcal Nuclease (MNase). Viral vector shedding results below the lower limit of quantification (BLQ) for each matrix are considered negative or “undetectable. [Section 6.3.8](#) describes the approach for handling results that are undetectable.

For each of the 5 viral vector level profiles, one without MNase treatment for whole blood, one without MNase for saliva, one with MNase for saliva, one without MNase for urine, and one with MNase for urine, the following endpoints will be determined:

- Peak viral vector levels (vg/ml) post fordadistrogene movaparvovec administration.

Defined as the largest detectable result collected prior to the first set of 2 consecutive negative results.

- Time in weeks to peak viral vector shedding post fordadistrogene movaparvovec administration.

Defined as the time in weeks from the date of fordadistrogene movaparvovec administration to the peak viral vector result defined above.

- Time in weeks to undetectable viral vector (time to clearance of viral vector) from date of fordadistrogene movaparvovec administration.

The first set of 2 consecutive negative results is identified and then time to undetectable viral vector is defined as the time in weeks from the date of fordadistrogene movaparvovec administration to the first of the 2 consecutive negative results identified. If at the time of analysis, the last result is positive or negative results have not been confirmed, the time is recorded at the last date on which a sample for the particular matrix occurs and will be marked as censored for the analysis, meaning the time to undetectable viral vector clearance is at least that value.

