Response to each of the 5 dimensions of the EQ-5D-5L assessment at Week 52 (caregivers of participants)	Summary Shift table	Caregivers of participants in the All Randomized	All available data will be included Missing data will not be imputed	N/A
Change from baseline at Week 52 in the EQ-5D-5L VAS assessment (caregivers of participants)	Summary	Caregivers of participants in the All Randomized	All available data will be included Missing data will not be imputed	N/A
Change from baseline at Week 52 in the EQ-5D-5L index score (caregivers of participants)	Summary	Caregivers of participants in the All Randomized	All available data will be included Missing data will not be imputed	N/A
Immune response				
ADA to mini-dystrophin	Summary	Safety Analysis Set (through Week 52)	All available data will be included Missing data will not be imputed	N/A
T cell response to mini-dystrophin by peptide pool	Summary	Safety Analysis Set (through Week 52)	All available data will be included Missing data will not be imputed	N/A
ADA to AAV9	Summary Box-plots for observed levels	Safety Analysis Set (through Week 52)	All available data will be included Missing data will not be imputed	N/A
NAb to AAV9	Summary Box-plots for observed levels	Safety Analysis Set (through Week 52)	All available data will be included Missing data will not be imputed	N/A

Endpoint	Analysis Type	Population	Data Inclusion and Rules for Handling Intercurrent Events and Missing Data	Analysis Model
T cell response to AAV9 by peptide pool	Summary Box-plots for observed levels	Safety Analysis Set (through Week 52)	All available data will be included Missing data will not be imputed	N/A
Viral Vector Shedding For each of the matrices: blood, saliva, urine				
Viral vector shedding	Summary	Viral Vector Shedding subset of Safety Analysis Set (through Week 52)	All available data will be included Missing data will not be imputed	N/A
Peak viral vector shedding	Summary	Viral Vector Shedding subset of Safety Analysis Set (through Week 52)	All available data will be included Missing data will not be imputed	N/A
Time of peak viral vector shedding	Summary	Viral Vector Shedding subset of Safety Analysis Set (through Week 52)	All available data will be included Missing data will not be imputed	N/A

090177e1a0727983\Approved\Approved On: 16-Apr-2024 16:39 (GMT)

Endpoint	Analysis Type	Population	Data Inclusion and Rules for Handling Intercurrent Events and Missing Data	Analysis Model

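### Peak viral vector level is still summarised without regard to assay, although vector levels were dropped because they may come from two assays that differ

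*SAP*

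**What the plan says.** The version 9 entry in SAP Section 1 reports the transfer of the shedding assay to an internal laboratory during the study and "some differences in the results between the 2 assays". It gives the consequence as "the analysis for endpoint viral vector levels are removed from the planned analysis as they may include data from both assays", and names Section 6.3.8 and Appendix 1 as the places changed.

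Section 6.3.8 retains four parameters, each for five profiles (whole blood without MNase; saliva and urine each with and without MNase):

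- "Peak viral vector levels (vg/ml) post fordadistrogene movaparvovec administration for each of the five profiles", summarised by N, mean, SD, median, quartiles and range;
- time to peak, summarised in the same way;
- "Time in weeks to undetectable viral vector (time to clearance of viral vector) from date of fordadistrogene movaparvovec administration for each of the five profiles", summarised by Kaplan-Meier;
- time to last undetectable, also by Kaplan-Meier.

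Section 3.3.4 defines peak level: "Defined as the largest detectable result collected prior to the first set of 2 consecutive negative results". It also states that "results below the lower limit of quantification (BLQ) for each matrix are considered negative". Appendix 1 keeps a row for "Peak viral vector shedding" and rows for the three times. It also has a general summary row for shedding as such, which no analysis in the current Section 6.3.8 corresponds to.

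**The concern.** The sponsor judged that a possible mixture of two differing assays was reason enough not to summarise vector levels. Peak level is one of those levels, in the same unit, selected as the largest per boy. If the mixture spoils a summary of levels, it spoils a mean and SD of peaks taken across assays.

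The clearance times come from the same results through a positive/negative call. That call is tied to the matrix and does not mention the assay. If the two assays have different limits, or read differently near the limit, the same true concentration could be positive on one and negative on the other.

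What is at stake is the interpretation of the shedding results, which answer a stated exploratory objective. A reader of the peak table could not tell how much of its location and spread comes from the product and how much from the laboratory.

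**Working it through.** The SAP gives no figure to reproduce: neither the assay difference nor the share of samples on each assay. The check is therefore a comparison of sections, followed by an illustration on stated assumptions.

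**Is there any assay-specific rule?**

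- Profiles (Sections 3.3.4 and 6.3.8): split by matrix and MNase treatment only.
- Viral Vector Shedding population (Section 4): defined for each matrix, not for each assay.
- Peak (Section 3.3.4): largest detectable result, assay not mentioned.
- Negative result (Section 3.3.4): defined for each matrix.
- Kaplan-Meier summaries (Section 6.3.8): no stratum or restriction by assay.
- Several values in one window (Appendix 2.1): the largest is used, whichever assay produced it.

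No section splits, restricts, bridges or flags results by assay.

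**Which parameters are exposed, and when?**

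- Peak level: whenever the boys' peaks do not all come from one assay.
- Time to undetectable and time to last undetectable: only if the assays differ in, or near, their limits of quantification.
- Time to peak: this depends on ranking results within one boy. A constant fold difference leaves the ranking unchanged unless that boy's own samples span both assays.

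**Illustration for peak.** Let p be the share of peaks from assay B and r its reading relative to assay A, with the same true peaks on both. The pooled arithmetic mean relative to assay A alone is (1 − p) + p·r.

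| p | r = 0.5 | r = 2 |
|---|---|---|
| 0.10 | 0.90 + 0.05 = 0.95 | 0.90 + 0.20 = 1.10 |
| 0.30 | 0.70 + 0.15 = 0.85 | 0.70 + 0.60 = 1.30 |
| 0.50 | 0.50 + 0.25 = 0.75 | 0.50 + 1.00 = 1.50 |

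**Illustration for clearance.** If a differently classified sample moves the event by one scheduled visit, the time changes by the gap between adjacent Appendix 2.1 target days, divided by 7.

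- Whole blood from Day 21 (21, 60, 90, 120, 240, 360): 39/7 = 5.6, 30/7 = 4.3, 30/7 = 4.3, 120/7 = 17.1 and 120/7 = 17.1 weeks.
- Urine and saliva, Days 1 to 34 (1, 2, 4, 7, 10, 14, 21, 34): from 1/7 = 0.1 to 13/7 = 1.9 weeks. Later gaps are 26/7 = 3.7, then 4.3, 4.3, 17.1 and 17.1 weeks.

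Under first-order decline, an f-fold difference in limit shifts the crossing time by half-life × log2(f). With an assumed half-life of 1 to 4 weeks, f = 2 gives 1.0 to 4.0 weeks and f = 10 gives 3.3 to 13.3 weeks.

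**The case against.** The strongest objection is that the plan describes a possibility, not an established mixture. Section 1 says only that the data may include both assays. It does not say how many samples are affected, in which matrix, in which direction, or whether any boy's profile spans the transfer. About 30 boys on active product are sampled, and collection in a matrix stops after two consecutive negatives, so mixing could be slight. All of this stands.

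A reader might infer that the retained parameters are in fact pooled over two qPCR assays and that none can be attributed to the product. The documents do not support this. The extent of mixing is unknown, and that both assays are qPCR is only an inference from Section 3.3.4.

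A reader might also infer that a boy can appear to clear on the day the assay changed. That needs a difference in or near the limits of quantification, which the SAP does not report. The definition of a negative result does not exclude each laboratory using its own limit, and clearance requires two consecutive negatives, so one discordant sample need not create an event.

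Finally, shedding is exploratory, has no estimand, is assayed in Cohort 1 only, and carries no test or decision rule. That limits the importance of the point.

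None of this removes the inconsistency for peak level. The possibility that the sponsor accepted as sufficient for levels is the same possibility for their maximum, and the plan does not say that the peaks come from one assay.

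**Conclusion.** The point holds in a limited form. The reason given for removing vector levels applies directly to peak level, which Section 6.3.8 still summarises without regard to assay. The two clearance times are conditionally exposed, and time to peak only for boys measured on both assays.

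The size cannot be determined from the SAP. The 0.75 to 1.50 range for the pooled mean peak rests on an assumed two-fold difference, an assumed 10% to 50% share and equal true peaks. The clearance shifts rest on an assumed reclassification by one visit, or on an assumed half-life and ratio of limits. They show that the effect could be material, not that it occurred.

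No primary or key secondary conclusion depends on these summaries. The change is worth making because it is cheap and the present text is at odds with its own rationale.

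**What to change.** In Section 6.3.8 and Appendix 1:

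1. Carry an assay identifier on every shedding result.
2. Summarise peak level by the assay that produced the peak. Give no mean or SD across assays unless bridging data are cited that justify pooling.
3. Keep the Kaplan-Meier summaries of both clearance times on all profiles, and report how many profiles span both assays.
4. Add a sensitivity summary of time to peak and both clearance times, restricted to profiles measured throughout by one assay.
5. Remove the general shedding summary row in Appendix 1, or reconcile it with Section 6.3.8.

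Do not add a rule that censors boys whose two negatives fall either side of the transfer. Sampling stops after two negatives, so such a boy may have no later sample. Observed clearances would then be censored because of their outcome, which would lengthen the Kaplan-Meier times.

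The cost is SAP wording, one identifier and a few tables from data already held. The drawback is a smaller N per table among the roughly 30 treated boys sampled; the SAP does not give the split between assays.
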